10.1 ADVERSE EVENTS

AEs will be coded using the *Medical Dictionary for Regulatory Activities* and reported separated for placebo lead-in, randomized treatment, and safety follow-up periods.

[figure not shown]
An AE (classified by preferred term) will be considered a treatment-emergent adverse event (TEAE) if it was not present before the first dose of DB IP (i.e. the first IP during the placebo lead-in period) or was present before the date of the first dose of DB IP and increased in severity after the first dose of DB IP. An AE that becomes serious after the date of the first dose of DB IP will also be considered as TEAE. If more than 1 AE was reported before the first dose of DB IP and coded to the same preferred term, the AE with the greatest severity will be used for comparison with the AEs occurring during each study period analyzed. An AE that occurred more than 30 days after the date of the last dose of DB IP (including the randomized IP) will not be considered as a TEAE.

[figure not shown]
The number and percentage of patients reporting TEAEs and TEAEs leading to study discontinuation in each treatment group will be tabulated by system organ class and preferred term and further categorized by severity and causal relationship to the IP. If more than 1 AE is coded to the same preferred term for the same patient, the patient will be counted only once for that preferred term using the greatest severity and strictest causality for the summarization by severity and causal relationship.

The incidence of common ($\geq 2\%$ of patients in any treatment group) TEAEs will be summarized by preferred term and treatment group and sorted by decreasing frequency for the test treatment.

A serious adverse event (SAE) that occurred between the date of the first dose of DB IP and 30 days after the date of the last dose of DB IP, inclusive, will be considered a treatment-emergent SAE (TESAE). The number and percentage of patients who have TESAEs will be summarized by preferred term and treatment group.

[figure not shown]
Listings will be presented for patients with SAEs, patients with AEs leading to discontinuation, and patients who die (if any). All patients with SAEs, including SAEs reported during the screening period and the safety follow-up period, and patients discontinuing because of AEs occurring before the start of randomized IP will be included in these listings.

[figure not shown]

[figure not shown]

[figure not shown]

RESTRICTED

RESTRICTED

12.0 INTERIM ANALYSIS

At the time of preparation for the Protocol Addendum Amendment 2, a blinded interim analysis was performed as part of data quality review as the study was progressing. In this review, it was observed that the standard deviation for the primary and secondary endpoints were substantially lower than the originally assumed values for sample size calculations. The observed standard deviations in the blinded reviews of this study and other ongoing acute studies at the same time (RAP-MD-02, and RAP-MD-03) were taken into considerations for revising the sample size estimation in next section (Determination of Sample Size).

13.0

DETERMINATION OF SAMPLE SIZE

The originally proposed primary efficacy variable is the change from baseline (ie., Day 7) at Day 8 in MADRS total score and the primary analysis population included the subset of patients who were placebo non-responders during the placebo lead-in period before randomization. Based on that the study was planned to randomize 700 patients (including both placebo responders and placebo non-responders), assuming standard deviation (SD) of 10 points, which provides 99% power to detect a difference of 3.25 points in MADRS total score between rapastinel 450 mg and placebo at a 2-sided significance level of 0.05.

While the study was ongoing, the primary efficacy variable was revised to be the change from baseline in MADRS score at the last visit, Day 21, and the primary efficacy study population was revised to include all randomized patients (placebo responders and placebo non-responders) based on the feedback by the FDA, EMA, and PDMA. Both of these changes were included in Amendment 2 of the protocol. At the same time of Amendment 2, a blinded data review was conducted for Studies RAP-MD-01, RAP-MD-02, and RAP-MD-03. The pooled SD for the three studies were 7.4, 8.0, and 8.7, respectively, all smaller than the originally assumed 10 points. Sample size was re-calculated using 8.7 as the common SD. The calculation used MMRM model with simulations; it also assumed correlation of 0.5 between the repeated measures and a common drop-out rate of 10% during the randomized treatment period and an additional 5% drop-out rate during the placebo lead-in period for all treatment groups. To have 90% power, the total sample size required is 360 patients. However, the study had already enrolled more than 440 patients with less than 5% of overall drop-out rate, surpassing the re-estimated sample size of 360 patients. The study enrollment was halted as soon as operationally feasible. The final sample size is approximately 460 patients (230 patients per treatment group).

14.0 STATISTICAL SOFTWARE

Statistical analyses will be performed in [REDACTED]

RESTRICITED

15.0

DATA HANDLING CONVENTIONS

15.1

VISIT TIME WINDOWS

Table 15.1–1 presents visits assigned and the corresponding range of treatment days (window) during which an actual visit may occur for all safety analyses where baseline is the last nonmissing assessment before the first dose of DB IP in the placebo lead-in period. The visit windows used in the “change from Day 0” or “reduction from Day 0” efficacy analyses will be derived according to this table as well. Termination visit is assigned to the visit window according to the table below.

Table 15.1–1. **Visit Time Windows for Change from Day 0 in Efficacy and Change from Baseline in Safety Analyses**

Analysis Visit	Target Date	Analysis Window (Based on Date)
Baseline	Index0 ^a	Last record on or before Index0 ^a
Day 1	Index0 ^a +1	Index0 ^a +1
Day 4	Index0 ^a +4	[Index0 ^a +2, IndexA ^b -1]
Day 7	IndexA ^b	IndexA ^b
Day 8 ^d	IndexA ^b +1	IndexA ^b +1
Day 11	IndexA ^b +4	[IndexA ^b +2, IndexB ^c -1]
Day 14	IndexB ^c	IndexB ^c
Day 15 ^d	IndexB ^c +1	IndexB ^c +1
Day 18	IndexB ^c +4	[IndexB ^c +2, IndexB ^c +5]
Day 21 ^{de}	IndexB ^c +7	Days [IndexB ^c +6, day of final double-blind visit or Early-termination Visit occurring after IndexB ^c +5]
Day 28	IndexB ^c +14	Within the safety follow-up phase

a Index0: Date of placebo dose during the placebo lead-in period

b IndexA: Date of first randomized dose or Index0 + 7 for patients who did not receive any randomized dose

c IndexB: Date of second randomized dose or IndexA + 7 if the 2nd dosing of randomized treatment was not administered for patients who were randomized

d For analysis of parameters

the visit windows for Days 1 and 8 will be extended to cover the next dosing day (indexA and indexB, respectively); the visit window for Day 15 will be 1 day after IndexB to Day 19; and the visit window for Day 21 will be Days 20 to the last double-blind visit, inclusively.

For efficacy analysis where baseline is defined as the last measurement prior to the first dose of randomized IP, the assigned visit and the corresponding range of treatment days (window) during which an actual visit may occur is displayed in **Table 15.1–2**. Termination visit is assigned to the visit window according to the table below.

Table 15.1–2. Visit Time Windows for Change from Baseline in Efficacy Analyses

Analysis Visit	Target Date	Analysis Window (Based on Date)
Day 0	Index0 ^a	Last record on or before Index0 ^a
Baseline	IndexA ^b	Last record on or before IndexA ^b
Day 8	IndexA ^b +1	IndexA ^b +1
Day 11	IndexA ^b +4	[IndexA ^b +2, IndexB ^c -1]
Day 14	IndexB ^c	IndexB ^c
Day 15	IndexB ^c +1	IndexB ^c +1
Day 18	IndexB ^c +4	[IndexB ^c +2, IndexB ^c +5]
Day 21 ^e	IndexB ^c +7	Days [IndexB ^c +6, day of final double-blind visit or Early-termination Visit occurring after IndexB ^c +5]
Day 28	IndexB ^c +14	Within the safety follow-up phase

a Index0: Date of placebo dose during the placebo lead-in period

b IndexA: Date of first randomized dose or Index0 + 7 for patients who did not receive any randomized dose

c IndexB: Date of second randomized dose or IndexA +7 if the 2nd dosing of randomized treatment was not administered for patients who were randomized

If a patient has 2 or more non-missing assessments within the same window, the assessment closest to the target day will be used for analysis; if there are 2 closest assessments with the same number of days from the scheduled day, the later one will be used for analysis.

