9.1.2 Double-blind Treatment Period

Approximately 460 patients are planned for enrollment in the double-blind treatment period (230 patients each in the rapastinel 450 mg and placebo groups). Patients will be randomized in a ratio of 1:1 to 1 of 2 treatment groups: rapastinel 450 mg IV weekly or placebo IV weekly (both adjunctive to ongoing ADT).

During the double-blind treatment period, patients will have 3 study visits per week. The visits will occur in the following pattern: treatment day, 1 day following the treatment day, 4 days following the treatment day, and 7 days following the treatment day (which is the next treatment day). If necessary, study visits may be conducted up to 2 days before or after the scheduled visits with the exception of visits that are 24 hours apart (eg, Visits 2 and 3 must be conducted 1 day apart; similarly, Visits 5 and 6 as well as Visits 8 and 9 must be conducted 1 day apart). All patients who receive IP must complete Visit 11. Upon completion of the double-blind treatment period, patients are eligible to enter the RAP-MD-04 maintenance study. Patients who do not enter RAP-MD-04 will enter a 1-week safety follow-up period.

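### For the footnote d parameters, the fixed Day 19/Day 20 boundary can put an on-time Visit 11 in the Day 15 window and leave Day 21 empty when the last dose was given 2 days early

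*SAP*

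**What the plan says.** SAP Section 15.1, Table 15.1-1, gives the windows for safety analyses and for efficacy analyses of change from Day 0. Its anchors are dates of dosing: "Index0: Date of placebo dose during the placebo lead-in period"; IndexA, the first randomized dose; and "IndexB: Date of second randomized dose or IndexA + 7 if the 2nd dosing of randomized treatment was not administered". In the body of the table, Day 15 is IndexB+1 only, Day 18 is IndexB+2 to IndexB+5, and Day 21 opens at IndexB+6 and closes on the "day of final double-blind visit or Early-termination Visit occurring after" IndexB+5.

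Footnote d, attached to Days 8, 15 and 21, replaces some of these windows for a subset of parameters. It begins "For analysis of parameters", and the names that should follow are not in the public text. It extends Days 1 and 8 to the next dosing day, which is still dose-anchored. It then says that "the visit window for Day 15 will be 1 day after IndexB to Day 19" and that "the visit window for Day 21 will be Days 20 to the last double-blind visit, inclusively".

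Where several assessments share a window, Section 15.1 says that "the assessment closest to the target day will be used for analysis"; ties go to the later one.

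On timing, Protocol Section 9.1.2 says: "If necessary, study visits may be conducted up to 2 days before or after the scheduled visits". The exception concerns the spacing of Visits 2 and 3, 5 and 6, and 8 and 9, which must stay 1 day apart. Visit 8, the last dosing visit, can therefore move if Visit 9 moves with it.

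**The concern.** Footnote d mixes two clocks. Its Day 15 window opens relative to the last dose but closes on what reads as a fixed study day, and its Day 21 window opens on a fixed study day. When the last dose is early, the whole post-dose course shifts earlier and these limits do not shift with it. A patient who kept to the protocol and attended Visit 11 exactly 7 days after the last dose can then have no Day 21 value for these parameters.

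What happens to the Visit 11 reading depends on which other readings exist. If there is one nearer IndexB+1, the closest-to-target rule keeps that one and the Visit 11 reading is not used in the by-visit analysis. If there is none, a reading taken 7 days after dosing is reported as Day 15, whose target is 1 day after dosing. In both cases the missing Day 21 value is caused by visit timing: those left out are the patients whose last dose came earliest.

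**Working it through.** **Inputs.** The window limits and the multiple-assessment rule come from SAP Section 15.1. The 2-day tolerance and the visit pattern (next visit 7 days after a treatment day) come from Protocol Section 9.1.2. Dosing at Visits 2, 5 and 8 comes from Protocol Section 9.4.7. Day n is taken as Index0+n, because Table 15.1-1 sets Day 1 at Index0+1 and Day 4 at Index0+4.

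**Step 1: reproduce the footnote's boundary.** On the nominal schedule IndexB = Day 14. The table's limits are then IndexB+5 = 14+5 = Day 19 and IndexB+6 = 14+6 = Day 20. These match footnote d, so its limits agree with the table when the last dose is on schedule.

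**Step 2: move the last dose within tolerance.** Counting 2 days either side of scheduled Day 14, IndexB runs from Day 12 to Day 16. Visit 11 is set at IndexB+7.

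| IndexB | Visit 11 | Footnote d as written | Table body | Footnote d with IndexB+5 / IndexB+6 |
|---|---|---|---|---|
| Day 12 | Day 19 | Day 15 | Day 21 | Day 21 |
| Day 13 | Day 20 | Day 21 | Day 21 | Day 21 |
| Day 14 | Day 21 | Day 21 | Day 21 | Day 21 |
| Day 15 | Day 22 | Day 21 | Day 21 | Day 21 |
| Day 16 | Day 23 | Day 21 | Day 21 | Day 21 |

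Only the Day 12 dose fails. Its Day 21 window would open on Day 20, after the last double-blind visit on Day 19, so it is empty. Visit 11 on Day 19 is itself within 2 days of scheduled Day 21.

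**Step 3: mirror case.** With IndexB = Day 16, an assessment at IndexB+4 falls on Day 20 and enters the Day 21 window; the re-anchored footnote would put it in Day 15. If a Visit 11 value exists at IndexB+7, the closest-to-target rule keeps that one, so the mirror case matters when Visit 11 is missing.

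**Step 4: size, with tolerance counted from the scheduled day.** The share equals the probability that Visit 8 falls on Day 12. The timing patterns are assumptions.

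- 80% on time, 7.5% at each of ±1 day, 2.5% at each of ±2 days: 2.5%; 0.025 × 460 = 11.5, about 12.
- 60% on time, 15% at each of ±1 day, 5% at each of ±2 days: 5%; 0.05 × 460 = 23.
- All five days equally likely: 1/5 = 20%; 0.20 × 460 = 92.

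**Step 5: size, if tolerance accumulates from dose to dose.** Each of the two dose intervals is then 5 to 9 days, and the fault occurs when their sum is 12 or less. This holds for 6 of the 25 pairs: 5+5, 5+6, 6+5, 5+7, 7+5 and 6+6. Let p7, p6 and p5 be the probabilities of a 7-, 6- and 5-day interval. The share is p5² + 2·p5·p6 + 2·p5·p7 + p6².

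- 80% on time: 0.000625 + 0.00375 + 0.04 + 0.005625 = 0.05, or 5% (23 of 460).
- 60% on time: 0.0025 + 0.015 + 0.06 + 0.0225 = 0.10, or 10% (46).
- Uniform: 6/25 = 24% (about 110).

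With IndexB+5 and IndexB+6 as limits, the share is 0% under either reading.

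**The case against.** **Day 19 and Day 20 may be nominal shorthand.** The SAP does not define them as Index0+19 and Index0+20, its scheduled visits are named in Day x form, and the two numbers coincide with the table's IndexB+5 and IndexB+6 on the nominal schedule. This is plausible. But the table defines its windows by date, and nothing in the footnote tells a programmer to convert these numbers. If the shorthand was intended, writing it out settles the point.

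**The numbering could start at Day 1 on the lead-in dose date.** Visit 11 after a Day 12 dose (Index0+12) would then be numbered Day 20 and the example would not fail. The table's own targets do not support that numbering.

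**The consequence cannot be fully traced.** The parameter names and the Schedule of Evaluations are not visible, so one cannot tell whether these parameters were measured at Visit 9 or Visit 10. Footnote e, also attached to Day 21, is not visible and could modify that window. This stands. A reader might infer that the Visit 11 value is always discarded; the documents support only that it leaves the Day 21 window, after which its use depends on what else was measured.

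**Safety reporting has other routes.** If the parameters are safety measures, SAP Section 15.3 uses all postbaseline values for determining potentially clinically significant values and lists every assessment. It takes the last nonmissing value as end-of-study when end-of-study assessments are repeated or unscheduled visits occur. That may soften the effect on end-of-study safety summaries. It does not restore a scheduled Visit 11 value to a Day 21 by-visit summary.

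**The last dose might be thought to range over Days 10 to 18.** That requires the tolerance to accumulate from dose to dose. The ordinary reading of the protocol is 2 days around the scheduled visit, which gives Days 12 to 16, so the smaller shares are the ones to lead with.

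**Conclusion.** The point holds as a minor, bounded defect. As written, footnote d assigns an on-time Visit 11 to the Day 15 window and leaves Day 21 empty when the last dose is on Day 12, a day the protocol permits. When Visit 11 is 7 days after dosing, a last dose 1 day early does not trigger it.

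The size is about 2.5%, 5% or 20% of patients with tolerance counted from the scheduled day, and 5%, 10% or 24% if it accumulates. These figures assume the stated timing patterns, Visit 11 exactly 7 days after the last dose, day numbers counted from Index0, and no contrary rule in footnote e. The base of 460 is the planned enrolment; the number of patients assessed on these parameters may be smaller.

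Because the label is Day 21, a reader might infer that the primary endpoint is at risk. The documents do not support that. The primary and key secondary MADRS changes from baseline use Table 15.1-2, whose post-dose windows are all dose-anchored and which carries no footnote d.

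**What to change.** In footnote d, replace Day 19 with IndexB+5 as the end of the Day 15 window, and Day 20 with IndexB+6 as the start of the Day 21 window. These are the limits the body of Table 15.1-1 already uses to separate Day 18 from Day 21. A Visit 11 at IndexB+7 then falls in Day 21 for every permitted dose date, an IndexB+4 assessment after a Day 16 dose returns to the Day 15 window, and nothing changes for a patient dosed on Day 14.

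If nominal shorthand was intended all along, the same edit states it. The cost is one footnote and the matching program line, with no new data.

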9.4.11.2 Contraception

For purposes of this study, females will be considered of childbearing potential unless they are naturally postmenopausal or permanently sterilized (ie, hysterectomy). Natural menopause is defined as the permanent cessation of menstrual periods, determined retrospectively after a woman has experienced 12 months of amenorrhea without any other obvious pathological or physiological cause.

For women of childbearing potential and male partners of childbearing potential who may participate in the study, the following methods of contraception, if properly used, are generally considered reliable: hormonal contraceptives (ie, oral, patch, injection, implant), male condom with intravaginal spermicide, diaphragm or cervical cap with spermicide, vaginal contraceptive ring, intrauterine device, surgical sterilization (bilateral tubal ligation, bilateral salpingectomy), vasectomized partner, or sexual abstinence.

The Investigator and each patient will determine the appropriate method of contraception for the patient during the participation in the study.

See Section 9.5.2.3 for pregnancy reporting procedures.

9.4.12 **Monitoring Treatment Compliance**

IP compliance during any period will be closely monitored by capturing the date and time of each injection of IP. If a scheduled injection does not occur, the Sponsor must be notified and the reason captured in the eCRF.

Background ADT compliance will also be closely monitored. Patients should be questioned to determine if there were any missed doses or changes in dose at

Visits 2, 5, 8, and 11. Every effort should be made to have patients bring their background ADT to Visits 5, 8, and 11 for verification of patient-reported compliance by pill count (to the extent possible). Missed doses or other changes in the dose of ADT and the reason should be captured in the eCRF.

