5.3 MODIFIED INTENT-TO-TREAT POPULATION

The modified Intent-to-Treat (mITT) Population will consist of all patients who were randomized, received at least 1 dose of IP during the randomized treatment period, and had at least 1 post-randomization assessment of the MADRS total score.

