9.0 EFFICACY ANALYSES

All efficacy analyses will be based on the mITT Population, unless stated otherwise. The baseline for each specific efficacy endpoint is defined as the last measurement prior to the first dose of randomized treatment. The Day 0 measure for each specific efficacy endpoint is defined as the last measurement prior to the first dose of double-blind IP in the placebo lead-in period. The analyses for the placebo lead-in period will be presented for all patients combined and separately for the placebo responders vs. non-responders using the Enrolled Population. All statistical hypothesis tests will be performed at the 2-sided 5% significance level for main effects. All confidence intervals (CIs) will be 2-sided 95% CIs, unless stated otherwise.

For efficacy analyses in which study center is a factor, a *small center* will be defined as a center with less than 2 placebo non-responder patients in at least 1 treatment group in the mITT Population. Small centers will be pooled to form pseudo-centers so that each treatment group includes at least 2 placebo non-responder patients within the center for the mITT population. Pooling will be done using the following algorithm:

Based on the number of placebo non-responder mITT patients, small centers will be ordered from the largest to the smallest, and centers of the same size will be ordered from the largest center number to the smallest center number. The pooling process starts with the largest small center from the top, which will be pooled with the smallest from the bottom until a non-small center is formed. The process will be repeated using the small centers left out after the first pass. If any centers are left out at the end of the process, they will be pooled with the smallest pseudo-center. If there is more than 1 smallest pseudo-center, the pseudo-center with the smallest center number will be selected. In case the pseudo-center formed by pooling all small centers is still a small center, it will be pooled with the smallest non-small center. If there is more than 1 smallest non-small center, the one with the smallest center number will be selected.

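### SAP 15.1 visit indices omit the patient not injected at Visit 5 but injected at Visit 8; read literally, that patient's observed Visit 11 MADRS never reaches Day 21

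*SAP*

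**What the plan says.** SAP 15.1, Table 15.1-2, assigns MADRS records to analysis visits by two anchors. Footnote b: "IndexA: Date of first randomized dose or Index0 + 7 for patients who did not receive any randomized dose". Footnote c: "IndexB: Date of second randomized dose or IndexA +7 if the 2nd dosing of randomized treatment was not administered for patients who were randomized". Baseline is "Last record on or before IndexA". The Day 21 window runs from IndexB+6 to the "day of final double-blind visit or Early-termination Visit occurring after IndexB"+5, with target IndexB+7. Table 15.1-1 uses the same two indices.

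SAP 9.0 defines baseline in words: "The baseline for each specific efficacy endpoint is defined as the last measurement prior to the first dose of randomized treatment". SAP 9.1 makes change from baseline to Day 21 the primary parameter, analysed by MMRM on observed cases without imputation.

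Missed injections are foreseen. Protocol 9.4.12: "If a scheduled injection does not occur, the Sponsor must be notified and the reason captured in the eCRF". Protocol 9.1.2 requires Visit 11 of everyone who has received IP. SAP 5.3 admits to the mITT Population any randomized patient who "received at least 1 dose of IP during the randomized treatment period, and had at least 1 post-randomization assessment of the MADRS total score". The SAP's history of changes says that the index definitions were revised to deal with scheduled doses that were not given.

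**The concern.** Injections are given only at Visits 2, 5 and 8 (Protocol 9.4.7), and under the SAP design the Visit 2 dose is lead-in placebo. A patient whose first randomized injection is at Visit 8 therefore has no later visit at which to receive a second. Footnote b's fallback to Index0+7 is closed to this patient, who did receive a randomized dose. Footnote c's fallback applies, but it counts from an IndexA that is already a week late.

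The gap falls on a patient who matters for the primary analysis. Someone with no randomized dose gets correct labels but is outside mITT. Someone who misses only the second dose gets correct labels. Someone who misses only the first is in mITT, may complete Visit 11, and may still have no value at the primary time point. If this surfaces only after unblinding, the handling of primary-endpoint data becomes a post hoc choice.

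**Working it through.** **Inputs.** The visit pattern in Protocol 9.1.2 and the SAP 15.1 labels give Visit 2 = Day 0, Visit 5 = 7, Visit 6 = 8, Visit 7 = 11, Visit 8 = 14, Visit 9 = 15, Visit 10 = 18 and Visit 11 = 21. MADRS is assumed at every visit: Protocol 9.2 says that efficacy is assessed at each visit, but the schedule table is not shown. Visits may move by 2 days either way, with Visits 8 and 9 fixed 1 day apart (Protocol 9.1.2).

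**Step 1: dosing as scheduled.** IndexA = 7 and IndexB = 14. The Day 21 target is 14 + 7 = 21 and its window opens at 14 + 6 = 20, so Visit 11 supplies Day 21 and every other label is right. A patient dosed at Visit 5 only has IndexB = 7 + 7 = 14. A patient with no randomized dose has IndexA = 0 + 7 = 7 and IndexB = 14. Both get the same correct labels.

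**Step 2: dosed at Visit 8 only.** Read literally, IndexA = 14 and IndexB = 14 + 7 = 21. Reading the second dosing as the Visit 8 dosing gives IndexA = IndexB = 14.

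| Actual day (visit) | Literal reading | Alternative reading |
|---|---|---|
| 7 (V5), 8 (V6), 11 (V7) | unused | unused |
| 14 (V8) | Baseline | Baseline and Day 14 |
| 15 (V9) | Day 8 | Day 8 and Day 15 |
| 18 (V10) | Day 11 | Day 18 |
| 21 (V11) | Day 14 | Day 21 |
| Analysis visits left empty | Days 15, 18, 21 | Day 11 |

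On the literal reading the Day 21 window opens at 21 + 6 = Day 27, which is 6 days after Visit 11. On the alternative reading the Day 11 window would run from 14 + 2 = 16 to 14 - 1 = 13, so it contains no days. One record then serves both Day 8 and Day 15, and the Day 14 row repeats the baseline record. A third reading, in which the first randomized dose means the Visit 5 dose, leaves IndexA undefined.

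**Step 3: visit tolerance.** The latest Visit 11 is 21 + 2 = 23 and the earliest Visit 8 is 14 - 2 = 12, a gap of at most 11 days. On the literal reading the Day 21 window opens 7 + 6 = 13 days after Visit 8, so visits within tolerance cannot reach it. Day 21 was empty in all 95 admissible combinations of Visit 8, 10 and 11 dates. Off the nominal schedule, Visit 11 can instead land in Day 11, 15 or 18, or lose to Visit 10 within the Day 11 window.

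**Step 4: pattern-mixture analysis.** SAP 9.1 defines the pattern by the last visit with an observed value. On the nominal schedule and the literal reading that is Day 14, so a patient who completed Visit 11 is imputed at Days 15, 18 and 21 as a dropout.

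**Step 5: size.** No frequency is given. Purely as an assumption, 0.5% to 2% of 460 is 2.3 to 9.2 patients. For scale, approximate power is Φ(δ / (σ√(2/n)) - 1.96), with n per arm.

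- Check against the plan: n = 350, δ = 3.25, σ = 10 gives 0.990, matching the stated 99% (Protocol 9.7.9).
- n = 230, σ = 8.7, with δ = 3.25 assumed to carry over: 0.980.
- 2% without a Day 21 value (n = 225.4): 0.978.
- 5% without a Day 21 value (n = 218.5): 0.974.

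This calculation ignores what the MMRM recovers from other visits and any effect of the mislabelled values.

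**The case against.** The best defence is that the literal mapping keeps time relative to the first dose received. This disposes of several stronger conclusions that a reader might draw.

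- A reader might infer that the first key secondary endpoint is contaminated. It is not, on the SAP's own terms: SAP 4.0 and 9.2 describe Day 8 as 1 day after the first randomized treatment, which for this patient is actual Day 15.
- A reader might call the Day 14 baseline an error. It follows the definition in SAP 4.0 and 9.0.
- A reader might infer that every MADRS is filed a week early. Only those from Visit 8 on move; the Day 7, 8 and 11 scores are simply unused.
- A reader might infer that Table 15.1-1 corrupts the lead-in Day 4 row. The true Day 8 and Day 11 scores do fall inside that window, but the closest-to-target rule keeps the real Day 4 record. The row is affected only if that record is missing.

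Some text is also unavailable. Footnote e is marked on the Day 21 row but not shown. The visit-by-visit protocol descriptions and the Restricted Access Addendum are not available either, so a rule requiring withdrawal after one missed injection cannot be excluded. Protocol 9.3.3 lists noncompliance with IP among reasons for which a patient can be discontinued. The 2-day tolerance will also rescue some missed injections, so the sequence may be rare.

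These points limit the concern but do not remove it. Dose-relative time cannot supply the primary endpoint, which SAP 13.0 and Protocol 9.7.9 place at the last visit. The reading that rescues Day 21 breaks other rows.

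**Conclusion.** The gap is real and minor. For an mITT patient first injected at Visit 8, footnotes b and c give no workable set of windows. The literal reading leaves Day 21 empty although Visit 11 was attended, leaves the true Day 8 and Day 11 scores unused, and makes a completer look like a dropout. The alternative reading makes two windows coincide and leaves Day 11 without one.

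This rests on MADRS being collected at every visit, on such a patient being allowed to continue, and on footnote e not already resolving the case. The number of such patients is unknown; 2 to 9 is an illustration, not an estimate from the documents. A reader might infer a material threat to the primary result. The documents do not support that: even if 5% lost Day 21, approximate power would move only from 0.980 to 0.974. The reason to act is that observed primary-endpoint data are misfiled by a rule revised to handle missed doses.

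**What to change.** In footnotes b and c of Tables 15.1-1 and 15.1-2, anchor the indices to the scheduled treatment visits:

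- IndexA = date of Visit 5, whether or not the injection was given; Index0+7 if Visit 5 was not attended.
- IndexB = date of Visit 8, whether or not the injection was given; IndexA+7 if Visit 8 was not attended.

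For the patient above this gives IndexA = 7 and IndexB = 14. Every post-randomization score keeps its own label and Visit 11 supplies Day 21.

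Align the efficacy baseline to the last MADRS on or before IndexA and before any randomized dose. Without this, the revised table would give Day 7 while the wording in SAP 9.0 would still give Day 14. The wording sits in SAP 4.0, 9.0 and 15.1 and in Protocol 2.0 and 9.7.5, so more than one sentence changes. Record the change in SAP 16.0 before unblinding, and check it against footnote e.

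The cost is a few text edits and a small programming change; labels for patients dosed on schedule are unaffected. The downside is that, for these few patients, Day 8 is no longer 1 day after an actual randomized dose. That departs from the literal key secondary definition and should be stated, but it fits the SAP 9.0 rule of analysing patients as randomized regardless of treatment received.
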